## 5. LIST OF ABBREVIATIONS AND DEFINITION OF TERMS

AE	Adverse Event
AESI	Adverse Event of Special Interest
ALT	Alanine aminotransferase
AST	Aspartate aminotransferase
ATC	Anatomical Therapeutic Chemical classification
BID	Bis in Die
BMI	Body Mass Index
BOR	Best Overall Response
BOCR	Best Overall Confirmed Response
BP	Blood Pressure
BSA	Body Surface Area
CK	Creatine Kinase
CI	Confidence Interval
COVID-19	Coronavirus Disease 2019
CR	Complete Response
CtDNA	Circulating tumor DNA
CT scan	Computed Tomography scan
DBP	Diastolic Blood Pressure
DI	Dose Intensity
eCRF	Electronic case report form
ECG	Electrocardiogram
EQ VAS	EuroQol Visual Analog Scale
ES	Efficacy Set
FA	Fluorescein Angiography
FAS	Full Analysis Set
FPFV	First Patient First Visit
HR	Heart Rate
ICH	International conference on harmonisation of technical requirements for registration of pharmaceuticals for human use
KM	Kaplan-Meier
LLT	Lowest Level Term
LPLV	Last Patient Last Visit
LVEF	Left Ventricular Ejection Fraction
MedDRA	Medical Dictionary for Regulatory Activities
MSI	MicroSatellite Instability
NGS	Next Generation Sequencing
OCT	Optical Coherence Tomography
ORR	Overall/Objective Response Rate
PD	Progressive Disease
PDI	Planned Dose Intensity
PFS	Progression-Free Survival
PGIC	Patient Global Impression Change

PK	Pharmacokinetic
PP	Per Protocol Set
PCR	Polymerase Chain Reaction
PR	Partial Response
PT	Preferred Term
QD	Quaque Die (once daily)
QoL	Quality of Life
QTcF	QT interval corrected for heart rate using Fridericia's formula
QW	Quaque Week (once a week)
Q2W	Quaque 2 Weeks (once every 2 weeks)
RBC	Red blood cells
RDI	Relative Dose Intensity
RECIST	Response Evaluation Criteria In Solid Tumours
SAE	Serious Adverse Event
SAP	Statistical Analysis Plan
SBP	Systolic Blood Pressure
SC	Steering Committee
SD	Stable Disease
StD	Standard Deviation
SEM	Standard Error of Mean
SOC	System Organ Class
SPC	Summary Of Product Characteristics
TA	Tumor Assessment
TEAE	Treatment Emergent Adverse Event
TESAE	Treatment Emergent Serious Adverse Event
ULN	Upper Limit Normal
USM	Urgent Safety Measure
VAS	Visual Analysis Scale
WBC	White Blood Cells
WHODrug	World Health Organisation Drug

## 6. INTRODUCTION

This document describes the interim and final statistical analyses of the study, including pharmacokinetic analysis, that will be performed after the Stage 1 and Stage 2 snapshots, and final lock of the clinical database.

This statistical analysis plan will be approved, finalised and signed before the first subject is screened in the study.

### 6.1. STUDY DESIGN

This Phase II study is conducted as an open-label, single arm, multinational, multicenter study of encorafenib, binimetinib plus cetuximab in subjects with previously untreated *BRAF*V600E-mutant Metastatic Colorectal Cancer.

The study will include two stages according to a two-stage design.

**Stage 1:** In the first stage, 40 subjects will be treated. In case of discordance in the results between the local assay and the central laboratory (potential false-positive local result), or lack of *BRAF*V600E confirmation, subject will be replaced for the interim primary analysis (futility analysis). If there are 11 or fewer confirmed responses (CR or PR) in the 40 treated subjects with a centrally confirmed *BRAF*V600E mutation, the study will be stopped. Otherwise, additional subjects will enter stage 2. Stage 2 may be initiated as soon as 40 subjects with a centrally confirmed *BRAF*V600E mutation are treated and confirmed responses are observed in at least 12 subjects.

**Stage 2:** 50 additional subjects will be treated, for a total of 90 subjects with a centrally confirmed *BRAF*V600E mutation. In case of discordance in the results between the local assay and the central laboratory (potential false-positive local result), or lack of *BRAF*V600E confirmation, subject enrolled in the stage two of the trial will be replaced for the primary analysis.

If at any time there is lack of confirmation of the *BRAF*V600E mutation in a total of 6 subjects ( $\geq 6\%$  of the total planned enrollment) or discordance between the local assay and the central laboratory in 3 subjects ( $\geq 3\%$  of the total planned enrollment), all subsequent subjects will be required to have

$BRAF^{V600E}$  determined by the central laboratory prior to study treatment assignment (i.e., local  $BRAF$  testing will no longer be accepted for trial eligibility).

Subjects will be eligible for the study based on identification of a  $BRAF^{V600E}$  mutation in the tumor tissue as determined by local laboratory result obtained at any time prior to Screening. Only polymerase chain reaction (PCR) and next generation sequencing (NGS)-based results will be acceptable. The BRAF mutation status must be confirmed by central laboratory no later than 30 days after the first dose of study treatment. In cases where there is a discordance between local assay and central laboratory results (i.e. either no BRAF mutation identified or not a  $BRAF^{V600E}$  mutation), or if the central laboratory is not able to confirm presence of a  $BRAF^{V600E}$  mutation due to inadequate or poor sample condition or absence of available material within 30 days of initiating study therapy, subjects may only continue treatment if there is no clinical indication of deterioration or disease progression and the Investigator determines that the subject is deriving benefit. In such instances, subjects must be informed that the  $BRAF^{V600E}$  mutation status is unconfirmed and must sign a separate informed consent form (ICF) that includes this information and describes alternative treatment options. Subjects with an unconfirmed  $BRAF^{V600E}$  mutation status will be included in the Full Analysis Set (when they have received at least one dose of study treatment (partial or full), cf. section 7).

Treatment will be administered in 28-day cycles until disease progression, unacceptable toxicity, subject's decision, withdrawal of consent, initiation of subsequent anticancer therapy or death. After discontinuation of study treatment, there will be a 30-day safety follow-up period. Subjects will then enter a survival follow-up period after the completed 30 days safety follow up and will be followed for at least 1 year after the start of study treatment of the last subject enrolled. If a subject discontinues the treatment for a reason other than progressive disease, tumor assessment must be performed (as per local and central review) until the start of new anti-cancer therapy, disease progression, death, lost to follow-up, subject decision or withdrawal consent.

The investigational products in this study are encorafenib and binimetinib in combination with cetuximab. Dose schedule is the following:

- Encorafenib: 300 mg PO (oral capsule 4X 75 mg) QD.
- Binimetinib: 45 mg PO (oral tablet 3X 15 mg) BID.
- Cetuximab: 400 mg/m^2 intravenous (IV) at Cycle 1 day 1 then 250 mg/m^2 IV every week (QW) for the first 28 weeks. Then, 500mg/m^2 IV every two weeks (Q2W) from week 29 (Cycle 8 day 1).

If there is a dose modification prior to switching to the biweekly schedule, the total dose per cycle should be maintained (i.e. 200mg/m^2 QW may be changed to a 400mg/m^2 Q2W).

The *end of the study* is defined as the time point when all subjects have been followed for at least 1 year after the start of study treatment of the last subject enrolled (including survival status).

## 6.2. STUDY OBJECTIVES

The **primary objective** of the study is to evaluate the antitumor activity of the combination of encorafenib, binimetinib and cetuximab by assessing the confirmed overall response rate (cORR) by local radiologist/investigator assessment in adult subjects with previously untreated centrally confirmed *BRAF* V600E-mutant (*BRAF*V600E) metastatic colorectal cancer (mCRC).

The **secondary objectives** of the study are:

- To evaluate the cORR by central radiologist assessment.
- To evaluate ORR (for confirmed and unconfirmed responses) by local radiologist/investigator and central assessment.
- To assess the effect of the combination of encorafenib, binimetinib and cetuximab on the duration of response (DOR).
- To assess the effect of the combination of encorafenib, binimetinib and cetuximab on other time-related efficacy parameters: time to response (TTR), progression-free survival (PFS) and overall survival (OS).

- To characterize the safety and tolerability of the combination of encorafenib, binimetinib and cetuximab.
- To assess the effect on quality of life (QoL).
- To explore health care resource utilization.
- To describe the pharmacokinetics (PK) of encorafenib, binimetinib, a metabolite of binimetinib (AR00426032) and cetuximab.

#### **Exploratory objectives:**

- To assess the relationship between changes in tumor markers (carcinoembryonic antigen [CEA] and carbohydrate antigen 19-9 [CA19-9]) and radiographic response to treatment.
- To assess *BRAF*V600E status in blood circulating tumor DNA (ctDNA) at baseline.
- To assess the potential predictive significance of the microsatellite instability (MSI) status in subjects with *BRAF*V600E mutant mCRC.
- To assess blood- and tissue-based predictive biomarkers of activity

### **6.3. STUDY ENDPOINTS**

#### **6.3.1. Primary endpoint**

The primary endpoint is the confirmed Objective Response Rate (cORR) as assessed by local radiologist/investigator review as per Response Evaluation Criteria in Solid Tumours (RECIST 1.1).

The cORR is defined as the number of subjects achieving a best overall confirmed response of CR or PR divided by the total number of analysed subjects.

#### **6.3.2. Secondary endpoints**

The following secondary efficacy endpoints will be determined:

- cORR as assessed by central radiologist review as per RECIST 1.1.
- ORR (for confirmed and unconfirmed responses) as per local radiologist/investigator-assessment.

- ORR (for confirmed and unconfirmed responses) as per central assessment.
- Overall survival (OS) defined as the time from first dose to death due to any cause. If a subject is not known to have died, survival will be censored at the date of last known date the subject was alive or at the cutoff date, whatever is earlier.
- Progression-free survival (PFS), defined as the time from first dose to the earliest documented date of disease progression or death due to any cause, assessed based on local radiologist/investigator review.
- PFS defined with tumor assessment assessed based on central review will be also used in a supportive analysis of PFS.
- Duration of response (DOR) defined as the time from first radiographic evidence of response assessed based on local radiologist/investigator review to the earliest documented PD or death due to underlying disease and is calculated for responders only. Responders who do not have a PD or death date by the data cutoff date will be censored for DOR at their last adequate tumor assessment of CR, PR or SD prior to the cutoff date.
- Duration of response assessed based on central radiologist review.
- Time to response (TTR) defined as the time from first dose until first documented radiographic evidence of response of CR or PR assessed based on local radiologist/investigator review. Subjects who do not have a CR or PR by the cutoff date will be censored for TTR at their last adequate tumor assessment date if they didn't have a PFS event, and at maximum follow-up (i.e. FPFV to LPLV used for the analysis) if they had a PFS event.
- Time to response assessed based on central review.
- Type and severity of adverse events (AEs) and serious adverse events (SAEs), changes in hematology and chemistry values, physical examinations, vital signs, electrocardiogram (ECGs) and echocardiogram (ECHO)/ multi-gated acquisition (MUGA) scans and ophthalmological examinations graded according to the National Cancer Institute Common Terminology Criteria for Adverse Events v4.03 (NCI-CTCAE v4.03).
- Change from baseline in the European Organization for Research and Treatment of Cancer (EORTC) Quality of Life Questionnaire for Cancer subjects (QLQ-C30), EuroQol-5D-5L (EQ-5D-5L), and Patient Global Impression of Change (PGIC).
- Resource utilization focused on hospitalizations occurring during the study treatment phase.

- Plasma concentrations of encorafenib, binimetinib and the active metabolite of binimetinib (AR00426032) and serum concentration of cetuximab.

### 6.3.3. Exploratory endpoints

The following exploratory efficacy endpoints will be determined:

- Changes from baseline in blood tumor markers (carcinoembryonic antigen [CEA] and carbohydrate antigen 19-9 [CA19-9]) at the beginning of each cycle and at the end of treatment.
- *BRAF*V600E mutation status in blood circulating tumor DNA (ct-DNA) at baseline.
- MSI status in formalin-fixed paraffin-embedded (FFPE) samples via established PCR assays in tumor sample versus germline control at screening.

## 6.4. STUDY TIMEPOINTS

**Table 1: Study Timepoints**

Analysis Visit Number	Study Phase Number	Study Phase	Visit Label for Statistical Output
1	1	Screening	Screening
x.1	2	Treatment	CxD1
x.2			CxD8
x.3			CxD15
x.4			CxD22
901			End of treatment
902			Safety follow-up
91y	3	Long-term follow-up	Survival y

## 6.5. SAMPLE SIZE

The sample size is based on a two-stage design with nominal risks  $\alpha=2.5\%$  and  $\beta=20\%$ .

The null hypothesis that the true response rate is 30% will be tested against a one-sided alternative. In the first stage, 40 subjects will be treated. Subjects in whom the presence of  $BRAF^{V600E}$  is not confirmed (discordance or lack confirmation) by central laboratory will be replaced. If there are 11 or fewer confirmed responses in these 40 treated subjects, inactivity will be declared, and the study will be stopped for futility.

The time point for the futility analysis will be after all 40 treated patients of stage 1 with centrally confirmed  $BRAF^{V600E}$  mutation had the opportunity to complete four post baseline tumor assessment. And in case the last subject required for the concerned stage has an objective response, it should be confirmed in the following tumor assessment before the analysis is being performed. However, it will be possible to proceed to Stage 2 as soon as 40 subjects with a centrally confirmed  $BRAF^{V600E}$  mutation are treated and 12 confirmed responses are observed.

Subjects data that will be analyzed during the futility analysis will be reviewed on an ongoing basis in order to determine as soon as possible (even before the inclusion of the 40th patient) whether the criteria for continuing to stage 2 (12 confirmed responses) are satisfied or not.

As it may take several treatment cycles for subjects to achieve a confirmed response, then a limited number of subjects (maximum 12) from stage 2 may be treated while waiting for all subjects in the initial cohort of 40 subjects in Stage 1 to be evaluable for a confirmed response. These additional subjects will not count towards responses in Stage 1 but will be included as part of the Stage 2 cohort, should the study move forward into Stage 2.

If at any time it becomes evident that the threshold of 12 responses is unlikely to be met, then additional patients may not be recruited (e.g.: 6 or fewer responses among 35 patients with sufficient follow-up [potential for at least 2 post-baseline assessments]).

---

 NB: This means that patients who discontinued are to be taken into account

If the study continues to the second stage, 50 additional subjects will be treated for a total of 90 subjects with a centrally confirmed  $BRAF^{V600E}$  mutation.

The null hypothesis will be rejected if 37 or more confirmed responses are observed in 90 treated subjects. This design yields a 1-sided type I error rate equal to 1.6% and power of 80% when the true response rate is 45%.

NB: Due to the time needed to get the central confirmation of the  $BRAF^{V600E}$  mutation, more than 90 subjects with centrally confirmed  $BRAF^{V600E}$  mutation may be treated. If so, the nominal alpha and power will be computed. The Clopper-Pearson (exact) binomial 95% confidence interval will be computed with 37 confirmed responders observed among the N patients and the lower limit will be compared to the clinically relevant response rate of 30%.

Moreover, the primary analysis at Stage 2 will be repeated when excluding the overrunning patients (i.e. on the 90 first treated subjects with a centrally confirmed  $BRAF^{V600E}$  mutation, see section 14.1.1) and differences between the two analyses will be discussed.

The cut-off for stage 2 analysis will be after all 90 treated patients of stage 1 and 2 with centrally confirmed  $BRAF^{V600E}$  mutation had the opportunity to complete four post-baseline tumor assessments, and after subjects with an initial objective response have had an opportunity to have a confirmation scan. The sample size calculation was based on binomial probabilities calculated in R (version 3.2.3).

This binomial design matches the O'Brien-Fleming design (O'Brien, 1979) for one sample obtained using East software (version 6.4) with a 1-sided type I error rate equal to 2.5% and a power of 81%.

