### 6.10. STUDY SCHEME

## 7. ANALYSIS SETS

The following analysis sets are defined:

- The **Screened subjects set (SCR)** consists of all subjects who have signed any informed consent.
- The **Full Analysis Set (FAS)** is composed of all subjects having received at least one dose of study treatment (partial or full). The analysis of efficacy, safety, quality of life, biomarkers and healthcare resource utilization will be done on the FAS.

*Note:* Partial dose is defined as at least one dose of encorafenib, binimetinib or cetuximab.

- The **Efficacy Set (ES)** is composed of all FAS subjects with a centrally confirmed  $BRAF^{V600E}$  mutation. The analysis of efficacy, including the primary analysis of the primary endpoint, will be done on the ES.
- The **Per Protocol set (PP set)** is composed of all FAS subjects without any major protocol deviations. The PP set will be defined prior to the database lock supporting the primary analysis, and will be used for the supportive analyses of primary efficacy endpoint. *Note:* In this SAP, the term “major protocol deviations” describes all deviations likely to significantly bias the interpretation of the primary efficacy endpoint results leading to exclusion of PP set. There may be protocol deviations identified as major by the clinical team (in CTMS) that will not lead to exclusion of PP set. All deviations recorded in CTMS will be reviewed prior to database snapshot/lock to identify any potential deviations leading to exclusion of PP set.

Continuation of the study despite  $BRAF^{V600E}$  -mutant status not centrally confirmed is allowed by the protocol (i.e. not a protocol deviation), provided the subject had signed the appropriate ICF. As the study investigates “encorafenib, binimetinib plus cetuximab in subjects with previously untreated  $BRAF^{V600E}$  -mutant Metastatic Colorectal Cancer”, subjects with no central confirmation of the  $BRAF^{V600E}$  -mutant status (i.e. unconfirmed or negative) will be excluded from the PP set.

- The **Pharmacokinetics Set (PK Set)** will consist of all subjects who receive at least 1 dose of encorafenib, binimetinib or cetuximab and who have at least 1 post-dose PK blood collection with associated bioanalytical results.

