**14.1.1. Primary Analysis**

The cORR will be provided with a corresponding Clopper-Pearson (exact) binomial 95% CI (Clopper CJ et al, 1934) for the ES. The two-stage method will be used to test the null hypothesis with the possibility of stopping accrual earlier for futility. If the observed cORR at the end of the first stage is less than 28% (i.e.,  $\leq 11$  confirmed CRs + PRs among 40 treated subjects with a centrally confirmed *BRAF*V600E mutation), then insufficient efficacy will be concluded. Otherwise, at the end of stage 2, if the observed cORR is  $\geq 41\%$  (i.e.,  $\geq 37$  confirmed responses among 90 treated subjects with a centrally confirmed *BRAF*V600E mutation), the null hypothesis will be rejected.

In case of  $N > 90$  subjects treated with a centrally confirmed *BRAF*V600E mutation, this analysis will be repeated for the Stage 2 analysis, when excluding the overrunning subjects (i.e. on the 90 first treated subjects with a centrally confirmed *BRAF*V600E mutation).

In addition to the Stage 1 and Stage 2 analyses, the analyses for cORR will also be conducted at the time of the end of study.

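### If more than 90 confirmed subjects are treated, the SAP's named primary analysis has no stated rejection rule

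*SAP*

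**What the plan says.** The decision rule in SAP 6.5 is: "The null hypothesis will be rejected if 37 or more confirmed responses are observed in 90 treated subjects". SAP 14.1.1 words it as a rate: "Otherwise, at the end of stage 2, if the observed cORR is" at least 41%, glossed as at least 37 of 90 confirmed subjects, the null is rejected.

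SAP 6.5 also accepts that waiting for central BRAF results may take the number of confirmed subjects above 90. In that case nominal alpha and power are to be computed. In addition, "The Clopper-Pearson (exact) binomial 95% confidence interval will be computed with 37 confirmed responders observed among the N patients". Its lower end is then set against 30%, with no action attached. Then: "Moreover, the primary analysis at Stage 2 will be repeated when excluding the overrunning patients", and "differences between the two analyses will be discussed".

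On the analysis set, SAP 7 says: "The analysis of efficacy, including the primary analysis of the primary endpoint, will be done on the ES". The Efficacy Set has no cap at 90, and Protocol 13.5 names the same set. The first-90 analysis is secondary to it: under SAP 14.1.1, "this analysis will be repeated for the Stage 2 analysis, when excluding the overrunning subjects".

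The Stage 2 cut-off in SAP 6.5 and Protocol 13.15 depends on 90 subjects having had the chance of four post-baseline scans. SAP 6.6 also ties it to 90. Protocol 13.1 gives no number. Protocol 13.3, 13.8.1.1 and 13.15 contain no provision for overrun.

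**The concern.** SAP 8 reserves causal interpretation for this one test. With more than 90 confirmed subjects, the analysis that the plan calls primary has no critical value of its own. The two forms of the rule part with one extra subject: 37/91 is 40.7%, so 37 responders satisfy the count but not the rate. The interval check uses a fixed 37, not the observed count, and nothing follows if its lower limit is 30% or less. If the full-set and first-90 results disagree, the plan offers only discussion. A result near the boundary could then have its verdict settled after the data are seen, in an open-label trial with investigator-assessed response.

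**Working it through.** **Inputs.** Null rate 30%, alternative 45%, stop at 11 or fewer of 40, reject at 37 or more of 90, nominal one-sided alpha 2.5% (SAP 6.5; Protocol 13.3). N is not given; N=91-103 is assumed. Stage 1 is unchanged and stage 2 has N-40 subjects. Overrunning subjects are assumed to respond at the same rate with complete follow-up.

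**Formulas.** Rejection probability with critical count r: sum over x=12 to 40 of P[Bin(40,p)=x] × P[Bin(N-40,p) ≥ r-x]. Clopper-Pearson lower limit L(r,N): the 2.5% quantile of Beta(r, N-r+1).

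**The plan's own figures.** For N=90 and r=37 the sum is 0.0161 at p=0.30 and 0.7985 at p=0.45, matching the stated 1.6% and 80%. The interval for 37/90 is 30.8% to 52.0%, as in Protocol 13.3.

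**Three candidate rules for N>90** (alpha at 30%, power at 45%, in %):

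| N | L(37,N) | 37 kept: alpha | 41% kept: count; alpha; power | Observed lower limit >30%: count; alpha; power |
|---|---|---|---|---|
| 91 | 30.48 | 1.93 | 38; 1.12; 76.35 | 37; 1.93; 82.22 |
| 92 | 30.12 | 2.31 | 38; 1.37; 78.99 | 37; 2.31; 84.37 |
| 93 | 29.78 | 2.74 | 39; 0.95; 75.46 | 38; 1.65; 81.41 |
| 95 | 29.11 | 3.79 | 39; 1.41; 80.60 | 38; 2.35; 85.60 |
| 98 | 28.16 | 5.84 | 41; 0.84; 76.43 | 39; 2.39; 86.71 |
| 101 | 27.27 | 8.53 | 42; 0.87; 78.16 | 40; 2.43; 87.73 |
| 103 | 26.70 | 10.68 | 43; 0.74; 77.35 | 41; 2.09; 87.11 |

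The 37/N check therefore falls below 30% from N=93, whatever is observed. Over N=91-103 the lower-limit rule has alpha of 1.65% to 2.43% and power of at least 81.41%.

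**How often the choice matters.** The chance that the all-N count is at least 37 but short of the 41% count is 8.3% (N=92) and 16.3% (N=93) at a 40% rate, and 5.4% and 10.8% at 45%.

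**Full set against first 90.** Let X be the first-90 count, with stage 1 passed, and Y the count among the other N-90. The verdicts differ with probability P(X≥37, X+Y<r) + P(X<37, X+Y≥r), where r is the lower-limit count. At a 40% rate:
- N=92: 6.63%, all from the full set alone rejecting.
- N=93: 5.22%, of which 1.77 points are first-90 alone.
- N=95: 9.45%, of which 0.64 points are first-90 alone.
- N=96: 7.85%, of which 2.27 points are first-90 alone.
- N=101: 13.5%.

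Across N=91-103 the range is about 3% to 14%. At 45% it is 4.5% (N=92) and 6.4% (N=95). The range over N is 0.7% to 2.3% at 50% and 0.3% to 1.4% at the 30% null.

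**If either analysis were allowed to reject.** Type I error is 1.9% to 2.7%, above 2.5% only at N=98 (2.59%) and N=101 (2.70%).

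**The case against.** The strongest reply is that the plan is not silent. The first-90 analysis applies the protocol's rule exactly as written, is pre-specified and will always be reported. Recomputing alpha and power alongside an interval for 37 of N suggests that 37 is meant to carry over, with its properties disclosed. Protocol 13.3 already notes that the lower limit at 37/90 clears 30%, so a lower-limit criterion is arguably implied.

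Part of this stands: a result under the protocol's 90-subject rule will exist. But both documents name the uncapped Efficacy Set as primary, the SAP calls the first-90 analysis a repeat, and no sentence makes 37, 41% or the lower limit the test for N>90.

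Three stronger readings are tempting and not supported:
- A reader might infer gross alpha inflation. Even letting either analysis reject gives at most 2.7% over the assumed range.
- A reader might infer that the SAP adopts 37 for N>90 and so accepts 3.8% or more. It computes an interval for 37/N but does not make 37 the rule.
- A reader might infer that both readable thresholds are simply worse than a lower-limit rule. At N=91-92 the count of 37 is the lower-limit rule, and the 41% reading has lower type I error at the price of power.

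One further objection shapes the fix. The confirmed response rate divides by everyone in the set (SAP 14.1), so overrunning subjects without full follow-up count as non-responders. With the cut-off tied to 90 subjects, letting all N decide could bias the rate downward.

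**Conclusion.** The point holds as a gap in the decision rule and should be fixed. For N>90 the named primary analysis has no stated rejection criterion, and the readings that the text allows give different counts. Keeping 37 exceeds the nominal 2.5% from N=93. Keeping 41% is conservative and mostly leaves power under 80%. Disagreement between the full set and the first 90 is more often, but not always, the full set alone rejecting.

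The consequence is limited. It arises only if N exceeds 90 and the result lies near the boundary; disagreement is rare at a true rate of 30% or 50%. The sizes rest on the assumed N=91-103 and on overrunning subjects having the same response rate and complete follow-up. The textual gap does not depend on these assumptions.

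**What to change.** In SAP 6.5 and 14.1.1, state that for N>90 the full Efficacy Set decides and the null is rejected when the Clopper-Pearson 95% lower limit of the observed result exceeds 30%. The critical counts are 37 for N=91-92, 38 for 93-95, 39 for 96-98, 40 for 99-101 and 41 for 102-103. This replaces the fixed 37/N check. State that the first-90 analysis is supportive and does not alter the verdict, and that 41% applies to N=90 only.

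In SAP 6.5 and 6.6 and Protocol 13.1 and 13.15, set the Stage 2 cut-off so that every Efficacy Set subject, not only 90, has had the chance of four post-baseline scans and a scan to confirm any response.

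Mirror the decision rule in Protocol 13.3 and 13.8.1.1; Protocol 13.1 requires an amendment for major changes to the primary analysis. Making the first 90 decide instead would also need a protocol change, because it departs from the Efficacy Set named in Protocol 13.5 and 13.8.1.1.

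The cost is a few sentences, a short table of counts, matching protocol wording and a short delay to the analysis. No extra patients are needed.
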